The main objective of this project will be to identify inflammatory reduction biomarkers linked to MAPK-dependent alterations after CBD administration, as well as other systemic effects on cell signaling pathways. Investigating the role of cell-specific biomarkers describing the molecular response to CBD-administration may open avenues for additional therapeutic strategies that can help reduce the burden of chronic musculoskeletal pain and other pain-related symptoms and comorbidities in people living with HIV (PLWH). The team proposes to study the effects of CBD on inflammation and chronic pain in PLWH by enrolling five persons with HIV who will provide blood samples before and after taking CBD for two months. In the process, the goal will be to establish the molecular role(s) of different immune cells using single cell RNA-sequencing. Preliminary data from this study are expected to pave the way for further investigations in larger clinical cohorts. The primary aim of this project will be to identify key inflammatory reduction biomarkers linked to MAPK-dependent alterations after CBD administration. Secondary outcomes include pain relief and reductions in pain-related symptoms. We will use a prospective pilot study design where patients will self-administer the investigational product (CBD-extract) for 60-days (2 months).

Specific Aim #1 – Determine the effects of CBD on chronic on quality of life in PLWH. We will compareQuality of Life (QoL) measures between treatment conditions, including pain and pain-related symptoms, if present.

Specific Aim #2 – Determine key biobehavioral mechanisms contributing to antiinflammatory and analgesic effects of CBD administration in PLWH. We hypothesize that change in molecular (alterations in cell signaling and reduction in inflammatory cytokines), psychological (reduction in pain-related fear and pain catastrophizing), and pain sensitivity regulation measures will be associated with pain relief, inflammation reduction, and reservoir shrinkage. We will quantify the shift in anti-inflammatory macrophage/monocyte population caused by CDB administration by examining gene expression at the single-cell level from the PBMC samples. This will allow us to accurately pinpoint gene under- or over-expression patterns at the RNA level (biomarkers), that are both induced by CBD administration in PLWH, and specific to different cells (e.g., monocytes, T cells, B cells, or other immune cells).

6. Research Plan

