Motivation to study single cells. The molecular and cellular changes underlying the inflammation mitigation caused by CBD-administration are largely unknown, and stand as a major challenge both for understanding its basic biology (e.g., pathways involved, molecular mechanisms) and for the urgent unmet need of reducing the long-term harm chronic inflammation causes in PLWH. Our hypothesis is that CBD alters monocyte migration capacity with MAPK-dependent alterations. We expect this alteration to have

chain-effects based on cellular cross-talk, i.e., that different PBMC cell types (such as Tcells and B-cells) might express specific CBD-induced phenotypes. We hypothesize CBD-alterations to reverberate along the whole immune-modulation system through cellular cross-talk. Given the complexity of the immune response, we deem traditional (bulk) RNA sequencing as insufficient for the task. Population-averaged genomic profiling cannot adequately unravel the inter-cellular regulation in situ. This study will leverage the efficiency of newly available single-cell technologies to create a powerful dataset unveiling the functional properties of thousands of individual cells.

Sample collection and processing. We plan to collect samples from five to seven patients over three time points: baseline (no CBD), and after one and two months of CBD-administration with 5,000 cells sequenced per sample. Five to seven patients (15 to 21 samples) will provide the transcriptomes of 75,000-105,000 single cells, a large dataset for scRNAseq. Immediately after collection, samples will be collected by TBD Lab technician to be processed for scRNAseq at UF ICBR (PBMC scRNAseq experiments are routinely run at ICBR).

Data analysis. During the post-processing period, single-cell reads (count matrices) will be filtered for quality control. Unsupervised clustering will isolate statistically robust populations of similar cells. Clusters will be visualized using Principal Component Analysis (PCA), t-Distributed Stochastic Neighbor Embedding (tSNE), and Uniform Manifold Approximation and Projection (UMAP). The most informative gene expression markers will be identified by a host of non-parametric tests (e.g., the Kolmogorov–Smirnov test), comparing a given cluster against either a nearby cluster or all other clusters. Clusters of cells will be annotated by using their marker genes/pathways⁻ and prior biological knowledge to characterize each sample's cell composition.

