CBD biomarker extraction. We will contrast clusters of the same cell type at baseline (no CBD) and their counterparts after CBD administration. The difference in gene expression, measured in fold change, p-value, and ratio of cell fraction expressing the marker gene, will determine the phenotypic effect of CBD. For each cell type, we expect to extract one or more sets of CBD-specific candidate biomarkers that together will determine a phenotypic CBD per cluster (cell type) signature.

Investigational Product & Dosing Schedule. [name] (Co-I) will oversee CBD dosage and administration.We will source the investigational product from the same batch of our hemp-extract CBD product that is being used in the original protocol under IND 147985, 'Efficacy of a controlled short-term trial of Cannabidiol (CBD) ingestion on reducing symptomatic response and facilitating recovery after induced muscle injury' (Source: SunFlora, Inc, [name])''. SunFlora is a third-party tested hemp-derived product manufacturing company. SunFlora is dedicated to producing high quality hemp-derived products formulated to be safely used by the public and are manufactured in accordance with the Food and Drug Administration (FDA) Current Good Manufacturing Practices (cGMP) for Dietary Supplements, 21 CFR Part 111. Their hemp derived products are assessed multiple times at production process control points throughout the manufacturing process. Dietary ingredients used in the manufacturing process are accompanied by certificates of analyses (CoAs) confirming their identity and specifications. All finished products are tested to ensure they meet specifications prior to being released for distribution. The label and all labeling satisfy FDA requirements found under 21 CFR 101.

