Each participant will be provided two 30mL bottles (2000mg CBD per bottle) with a syringe dropper during their initial (baseline) visit with instructions/demonstration to administer the solution under the tongue (0.5 cc ~1/2 dropper) twice per day (BID) 8-12 hours apart (morning and evening) at the prescribed daily dosage (63mg/day). The sublingual route of administration allows the product to be absorbed directly into venous circulation, and thus bypasses the liver and eliminates the consequences of first pass metabolism; ultimately increasing its bio-availability. The bioavailability of CBD administered orally (including sublingual) is estimated to be 13-19% and its half-life estimated to be around 18-32 hours.

Physical Discomforts and Intervention Risks:

In previous clinical trials using hemp-derived products administered orally (liquid or capsule) and swallowed, a small percentage of patients experienced tiredness, change in appetite and gastro-intestinal discomfort following ingestion. We will be using daily doses of hemp extract that are considerably lower than the daily doses used in the clinical trials. Therefore, the chance of our participants experiencing these side effects is minimal.

Occasionally one or more of the following potential side effects of taking blood samples may occur: pain, bruising, slight bleeding, light-headedness, fainting and (rarely) an infection. A trained technician will be drawing the blood.

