Participants will then be instructed on how to perform their own passive surveillance for identifying these side effects/adverse events and what to do if they experience any of them between study visits while they are ingesting the investigational product. Each participant will be provided a daily log chart to record their daily CBD doses for compliance and monitoring purposes. During the passive surveillance period participants will be instructed to contact study personnel if they experience any of the side effects/adverse events from the checklist provided at the baseline visit. Study personnel will then contact the study physician ([name]) for consultation. The side effects/adverse reactions will be triaged as mild, moderate or severe, and a determination will be made as to whether the side effect/adverse reaction is due to the investigational product or some other circumstance (e.g. food poisoning). If the event is determined to be due to the investigational product and graded moderate to severe by the study physician, the participant will then be instructed to stop participation and seek medical care by their primary physician or hospital. Any participant that reports a serious adverse event will be followed to full resolution.

Patients will be contacted weekly and asked about missing doses. We will take note of any missed dose. Approximately at days 15 and 45, patients will be asked to provide a picture, sent via text to the study phone, with a close up of their CDB bottles, so that we can verify the liquid level. Patients will be instructed to not include anything identifiable in the background. Patients will be also instructed to bring their CBD bottles at every visit after the first. In case of non compliance (e.g., the patient forgets to bring the bottle or does not send the picture), the PI will consider whether to withdraw the patient for the study.

Study personnel will perform a follow-up phone call at 1 week after completion from the study for continued safety monitoring. Study personnel will refer to the checklist to determine if the participant has experienced or is experiencing any side effects or adverse events using the safety monitoring guidelines. If the participant reports experiencing any of the side effects/adverse events from the checklist the study physician will be consulted immediately for guidance and the participant's condition will be followed until full resolution.

Experimental Procedures:

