Screening: Study coordinator will screen candidate to determine if they meet the inclusion criteria for the study. The baseline visit activity will be described to the patient. The patient will sign the consent form. Instruction/demonstration about CBD and dropper use will be provided.

Visit 1: Baseline Evaluation before CBD administration

Activities during visit 1:

- Patient reads and signs the consent form.
- Patient completes a brief form providing information (e.g. age, address, phone number, etc., health history).
- Measure of patient's height, weight, and vital signs (HR, blood pressure, body temperature).
- Patient completes a urine drug test
- Patient completes a urine pregnancy test is they have the ability to become pregnant
- Patient fills questionnaires: PASS (Pain Anxiety Symptom Scale; four dimensions of pain measured: cognitive anxiety, escape/avoidance, fearful appraisal, physiological anxiety), VAS (Pain Experience Visual Analogue Scales; anxiety, depression, anger), PSQI (Pittsburg Sleep Quality Index; self-report used to assess a subject's usual quality of sleep)
- A trained nurse or technician draws a blood sample
- The patient is given 2 30mL bottles with a syringe dropper with instructions/demonstration to take the solution under the tongue (0.5 cc ~1/2 dropper) twice per day (BID), 12 hours apart (morning and evening), at the prescribed daily dosage (62.5mg/day).
- The patient schedules the next test visits to the laboratory.
- The patient receives \$100 for completing this visit.

Visit 2: Follow-up after a month period of CBD administration

Activities during visit 2 (day 26-34):

- Measure vital signs of the patient as in visit 1.
- Questionnaire filling as in visit 1.
- Blood draw as in visit 1.
- The patient schedules the next test visits to the laboratory.
- The patient receives \$100 for completing this visit.

Visit 3: Follow-up after a two-month period of CBD administration

Activities during visit 3 (day 56-64):

- Measure vital signs of the patient as in visit 1.
- Questionnaire filling as in visit 1.
- Blood draw as in visit 1.
- The patient schedules the next test visits to the laboratory.
- The patient receives \$100 for completing this visit.

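### Visit 3 may fall as late as day 64, but planned dosing and the by-volume CBD supply both end at day 60, so a two-month sample could be drawn days after the last dose

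*Combined protocol and SAP*

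**What the plan says.** Section 5 (Specific Aims) states that patients will "self-administer the investigational product (CBD-extract) for 60-days (2 months").

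Section 6, Investigational Product & Dosing Schedule, sets the supply: "Each participant will be provided two 30mL bottles (2000mg CBD per bottle) with a syringe dropper". The instructed volume is 0.5 cc twice a day, and the daily dose is given there as 63 mg. The Visit 1 list repeats the two bottles and the volume, and gives the schedule as "twice per day (BID), 12 hours apart (morning and evening), at the prescribed daily dosage (62.5mg/day").

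The third visit is headed "Activities during visit 3 (day 56-64"). Visits 2 and 3 list vital signs, questionnaires, a blood draw, scheduling and payment. Dispensing appears only at visit 1.

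Sample collection and processing defines the samples as "baseline (no CBD), and after one and two months of CBD-administration with 5,000 cells sequenced per sample". CBD biomarker extraction says: "We will contrast clusters of the same cell type at baseline (no CBD) and their counterparts after CBD administration".

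Safety Monitoring and Stopping Criteria provides a "daily log chart to record their daily CBD doses for compliance and monitoring purposes", and adds: "Patients will be contacted weekly and asked about missing doses". Photographs of the bottles are due at about days 15 and 45, and bottles are brought to each later visit.

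**The concern.** Three stated quantities do not line up: planned duration (60 days), supply by volume (60 days), and the last permitted day of visit 3 (day 64). A participant who follows the volume instruction closely runs out at about day 60 and can still be drawn, within protocol, up to about 4 days later. The closest adherers are the most exposed to this.

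The third sample is meant to represent two months on CBD. A sample drawn days after the last dose still follows 60 days of treatment, but at a much lower drug level than one drawn while dosing. If expression follows the current level, such a sample understates the on-treatment change. With 5 to 7 participants, one late draw is 1/7 = 14% to 1/5 = 20% of the visit 3 samples, and the plan has no rule to identify it or set it aside. Visit 2 is not affected: at 1 mL per day, at least 60 - 34 = 26 mL remains at the end of its window.

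**Working it through.** **Inputs.** Two bottles of 30 mL and 2000 mg each, 0.5 mL twice daily, 63 mg/day and a half-life of 18 to 32 h (Investigational Product & Dosing Schedule); 62.5 mg/day (Visit 1); 60 days of dosing (Specific Aims); visit 3 on days 56 to 64 (Visit 3).

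**1. The plan's 60 days, reproduced.** Supply = (2 x 30 mL) / (2 x 0.5 mL per day) = 60 days, or 120 doses. This equals the planned duration exactly.

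**2. Supply by the stated mg dose.** Concentration = 4000 mg / 60 mL = 66.7 mg/mL, so 1 mL per day delivers 66.7 mg/day, slightly above both stated doses. At 63 mg/day, 4000 / 63 = 63.5 days. At 62.5 mg/day, 4000 / 62.5 = 64.0 days, which needs 62.5 / 66.7 / 2 = 0.47 mL per dose.

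**3. Window days after day 60.** Days 61, 62, 63 and 64: 4 of the 9 permitted days.

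**4. Gap at the draw.** The time of the first dose and the day numbering are not stated, so three cases are shown for a morning draw:

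| First dose | 120th dose | Gap, day 61 draw | Gap, day 64 draw |
|---|---|---|---|
| Evening, day 0 | Morning, day 60 | 24 h | 96 h |
| Morning, day 1 | Evening, day 60 | 12 h | 84 h |
| Evening, day 1 | Morning, day 61 | 0 h | 72 h |

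So day 61 may be effectively on drug, and the longest gap is 3 to 4 days.

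**5. Drug remaining.** Fraction = 0.5^(gap / half-life), for half-lives of 18 h and 32 h:
- 24 h: 40% and 59%
- 72 h: 6% and 21%
- 84 h: 4% and 16%
- 96 h: 2.5% and 12.5%

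**6. Missed doses that close the gap.** 64 days x 2 = 128 doses, against 120 supplied: 8 missed, or 8 / 128 = 6.25%.

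**7. Supply needed.** Dosing through day 64 takes 64 x 1 mL = 64 mL, which is 4 mL (4 x 66.7 = 267 mg) more than is dispensed. Dosing only through the morning of day 60 takes 118 to 120 doses over the three cases, or 59 to 60 mL, leaving 0 to 1 mL spare.

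**The case against.** The strongest reply is that the gap rests on one of two conflicting instructions. At the Visit 1 dose of 62.5 mg/day the bottles last to the final day of the window, and the volume is written as approximate. The 60 days can also be read as a nominal duration at the centre of a window of 60 plus or minus 4 days; nothing tells a participant to stop at day 60 with a visit pending. A few missed doses stretch the supply. This stands, and it makes the gap possible rather than certain. It does not remove it, because the volume is what participants are told and shown to take, and taken by volume the bottles are empty after 60 days whatever the duration was meant to convey.

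Second, the dose log, weekly calls and returned bottles would probably reveal a gap of days. That is fair. But they are described as compliance monitoring, are not said to record dose times, do not prevent the gap, and feed no analysis rule.

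Third, a reader might go on to infer a percentage dilution of the two-month contrast. The documents do not support one. They give no distribution of visit days and no link between drug level and expression. The contrast in CBD biomarker extraction is not limited to two-month samples; if visits 2 and 3 feed it with equal weight, any dilution is about halved.

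A reader might also infer that draws need a fixed clock time or a set interval after the dose. The documents show no confounding by time of day, so that is not part of this point.

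**Conclusion.** The mismatch is real, and small. If doses are taken by volume with few missed, a visit 3 sample drawn on about days 61 to 64 can be up to about 4 days off drug, with as little as 2.5% to 12.5% of the last level remaining. This rests on the protocol's half-life range, simple exponential decline, and an assumed first-dose time. The gap closes at 62.5 mg/day or with 8 missed doses, and nearly closes at 63 mg/day.

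The consequence for the expression results is unknown: zero if the effect outlasts the drug, and otherwise dependent on how many visits fall late and which samples enter the contrast. It would be wrong to conclude that the two-month samples will be off drug or that the study is compromised. The point is that an avoidable ambiguity in so small a sample can be removed at little cost.

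**What to change.** In Specific Aims and Experimental Procedures:

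1. Tell participants to keep dosing through the day of the visit 3 draw, restate the duration accordingly, and dispense enough for day 64. That is at least 4 mL more, in practice probably a third 30 mL bottle.
2. If no extra product is available, book visit 3 by day 60 where possible and keep days 61 to 64 as a fallback. A hard cut to days 56 to 60 is weaker: it shortens the window from 9 days to 5, raises the risk of a missed visit, and leaves 0 to 1 mL spare.
3. Record the date and time of the last dose at visits 2 and 3.
4. Repeat the contrast without visit 3 samples drawn more than 24 h after the last dose.

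Cost: up to one extra bottle and up to 4 more dosing days per person, or less flexible booking; one added entry at each follow-up visit; and one sensitivity run.

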Study Population. Our clinical population will be men and women (N=5 to 7) 21-60 years old who are currently living with HIV (under antiretroviral therapy for 5+ years with a suppressed viral load).

Recruitment strategy. Co-I [name] has extensive experience in HIV patient recruitment and will oversee the recruitment team, during the recruitment phase, as well as the safety monitoring. Five PLWH (men and women) will be primarily recruited from The SHARC Registry (IRB# 201400073), a UF-IRB-approved registry of over 600 HIV patients who have agreed to be contacted about future research. Written informed consent will be obtained, and blood will be collected at the UF CTRB clinical research center. Inclusion criteria are: ability to read English and provide written consent; willingness to take CBD and to participate in follow up for two months; older than 21 and younger than 60; under antiretroviral therapy for 5+ years and suppressed viral load (CD4 count <350cells/ml); patients must agree to practice acceptable methods of birth control, namely sterilization (female tubal ligation or occlusion, male vasectomy), long-acting reversible contraceptives (intrauterine devices, hormonal implants), short-acting hormonal methods (pill, mini pills, patch, shot, vaginal ring), and condoms.

The main exclusion criterion will be conditions/medications that may impair the immune response (e.g. rheumatoid arthritis, cancer, diabetes chronic infections, CAD, cellulitis, autoimmune diseases such as lupus, sarcoidosis, and all medications they may affect inflammation such as aspirin, steroids, statins);), pregnancy, and current marijuana or CBD use (urine drug screen). Further exclusion criteria will be: excluding subjects taking anti-seizure medicines, with any history of seizure disorder or head trauma, any history of hepatic/liver disease or renal disease, any history of cardiovascular diseases; women who are lactating (in addition to existing exclusion criteria for pregnancy). Co-I [name] (a physician) will review conditions/medications after the initial interview before the patient is enrolled to exclude risks of drug interactions or hepatotoxicity. UF/Shands staff and students will not be considered for enrollment. Presence of chronic pain will not be considered as a necessary condition for enrollment.

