Primary Outcomes: This study takes a single-cell perspective, i.e., we will collect a large number of cells from a small number of patients, and we will measure RNA expression per single cell (not per patient). Note that from the single cell point of view, the number of patients (5-7) is sufficient to derive statistically viable results, as we will collect 5,000 cells from each patient at each time point (total 75,000-105,000 cells). Each cell will be sequence individually to read the RNA expression from a panel of approximately 20,000 genes. Cells will be pooled from all patients, and clustered via unsupervised algorithms into clusters of different cell types (e.g. T cells, B cells, monocytes). Our primary outcomes will be the extraction of gene expression patterns (RNA) from specific immune cell types found in PBMC (e.g., B cells, T cells, monocytes). We will regress these gene markers against the variation in baseline inflammation (C-reactive protein, erythrocyte sedimentation rate, and procalcitonin). After CBD administration to obtain CBD-related biomarkers for inflammation reduction. The difference in gene expression will be measured in fold change, p-value, and ratio of cell fraction expressing the marker gene. These biomarker gene will be unique for each cell type. We expect to extract specific biomarkers for each cell type and understand how CBD alters gene expressions of different immune cells in a different way-overall, we expect the genes of the MAPK signaling pathway (MAPK families play an important role in complex cellular programs like proliferation, differentiation, development, transformation, and apoptosis) to be strongly altered.

Secondary Outcomes. Self-report pain ratings will be used to determine peak pain intensity and pain persistence. The brief pain inventory (BPI) will be used to self-report pain perception. The inventory consists of rating pain on a visual analog scale (VAS). A 10cm line is drawn with 0 (no pain) on the left pole and 10 (worst pain imaginable) on the right pole. The inventory asks participants to rate their level of pain by placing a slash on the line that best represents their current level of pain as well as pain at its worst, best and average over the past 24 hours. The highest worst pain intensity reported during the intervention will be recorded as the peak pain intensity.

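### The claim that 5–7 patients suffice rests on a count of cells, but each CBD contrast has only 5–7 independent within-patient changes, and no patient-level term is planned for its p-values

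*Combined protocol and SAP*

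**What the plan says.** Section 6 plans 5 to 7 patients sampled at "three time points: baseline (no CBD), and after one and two months of CBD-administration with 5,000 cells sequenced per sample". Primary Outcomes states that "we will measure RNA expression per single cell (not per patient"), and then that "from the single cell point of view, the number of patients (5-7) is sufficient to derive statistically viable results". The reason offered is the number of cells.

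Cells from all patients are pooled and clustered into cell types. For the CBD effect, the paragraph on CBD biomarker extraction says "We will contrast clusters of the same cell type at baseline (no CBD) and their counterparts after CBD administration", and then "The difference in gene expression, measured in fold change, p-value, and ratio of cell fraction expressing the marker gene, will determine the phenotypic effect". Primary Outcomes repeats these measures over roughly 20,000 genes and adds a regression: "We will regress these gene markers against the variation in baseline inflammation (C-reactive protein, erythrocyte sedimentation rate, and procalcitonin").

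The only test named anywhere is a Kolmogorov–Smirnov-type test under Data analysis, and it is for finding cluster markers. For the CBD contrast the plan gives no test, unit of analysis, pairing, patient effect, per-patient aggregation or multiplicity rule.

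**The concern.** CBD exposure is assigned to the patient and changes only between visits. C-reactive protein, erythrocyte sedimentation rate and procalcitonin likewise have one value per patient per visit. Cells from the same draw share that patient's biology on that day and the handling of that sample, so they are not independent replicates of a response to CBD. Sequencing more of them sharpens each sample's mean but adds no patients.

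Stable differences between patients largely cancel in a balanced before/after contrast. Variation of the same patient from visit to visit does not, and a test over cells takes it for signal. The primary outcome includes these p-values, and the plan expects pronounced changes in MAPK pathway genes. The data may also be used to plan a larger trial, which could then be built on false leads.

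**Working it through.** **Inputs from the plan:** 5 to 7 patients, 3 visits, 5,000 cells per sample, about 20,000 genes. **Assumptions, because the plan gives no values:** two-sided 5% level, 80% power, *m* = 50 or 500 cells of one type per sample, and an intraclass correlation (ICC, the patient-by-visit share of cell-level variance) of 0.001, 0.01 or 0.05.

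**1. The plan's own figure.** 5 × 3 × 5,000 = 75,000 and 7 × 3 × 5,000 = 105,000. The cell totals reproduce. The plan states no power, effect size or SD, so there is no power claim to reproduce.

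**2. Independent units.** Each contrast (baseline to month 1, baseline to month 2) has one change per patient, so 5 to 7 changes. The two contrasts share patients and baselines, so together they still rest on 5 to 7 independent units.

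**3. Error of a cell-level test with no CBD effect.** Design effect = 1 + (*m* − 1) × ICC. True type I error = 2 × [1 − Φ(1.96/√design effect)]. For example, *m* = 500 and ICC 0.01 give 1 + 499 × 0.01 = 5.99 and 1.96/√5.99 = 0.80, hence 42.3%. For Bonferroni over 20,000 null genes (z = 4.708), expected false genes = 20,000 × 2 × [1 − Φ(4.708/√design effect)], against an intended 0.05.

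| Cells of a type per sample | ICC | Design effect | True error at nominal 5% | False genes after Bonferroni |
|---|---|---|---|---|
| 50 | 0.001 | 1.05 | 5.6% | 0.09 |
| 50 | 0.01 | 1.49 | 10.8% | 2.3 |
| 50 | 0.05 | 3.45 | 29.1% | 225 |
| 500 | 0.001 | 1.50 | 10.9% | 2.4 |
| 500 | 0.01 | 5.99 | 42.3% | 1,088 |
| 500 | 0.05 | 25.95 | 70.0% | 7,107 |

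The last column applies one ICC to every gene. Sequencing more cells makes the error worse: at ICC 0.01 with 5,000 cells it is 78%. The number of patients does not enter the formula, so moving from 5 to 7 does not help.

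**4. Simulation with count data and no CBD effect.** Gamma-Poisson counts, 3,000 replicates, two visits, 10% patient-by-visit coefficient of variation (CV), cell-level dispersion 0.5. The rank-sum test is assumed because the plan names none.

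| Case | Rank-sum over cells | Paired t on patients |
|---|---|---|
| N = 5, gene mean 1, 500 cells | 31.5% | 5.1% |
| N = 5, gene mean 1, 50 cells | 8.5% | 5.4% |
| N = 5, gene mean 0.05, 500 cells | 7.7% | 4.6% |
| First case plus 30% stable patient variation | 30.3% | 3.9% |
| N = 7, gene mean 1, 500 cells | 31.4% | 4.6% |

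A separate simulation with normal data and 500 cells (1,000 runs each at N = 5 and N = 7) used the pooled Kolmogorov–Smirnov test. It rejected 4–5% of the time at ICC 0, 36–38% at 0.01 and 68–70% at 0.05. The paired t-test on patient means gave about 4–7%.

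**5. What 5–7 patients can detect.** From the noncentral t distribution, a paired t-test for one gene has 80% power for a mean change of 1.68 SD (N = 5), 1.44 SD (N = 6) or 1.27 SD (N = 7), where SD is that of the within-patient change. At Bonferroni over 20,000 genes the figures are about 21.5 SD (N = 5) and 7.8 SD (N = 7). The smallest two-sided p-value an exact signed-rank test can give at N = 5 is 2/2⁵ = 0.0625.

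**The case against.** The best reply is that the harm is conditional. The plan does not say that the CBD p-values are computed over cells, and measuring expression per cell describes the assay. The sufficiency sentence is also limited to the single-cell viewpoint and sits beside the clustering step, where cell count does matter. The first part stands: cell-level testing is an inference from the wording and from the cell-count justification. The narrow reading of the sentence does not stand, because the same section makes the CBD p-values part of the primary outcome.

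A second reply is that the p-value is read together with fold change and the fraction of expressing cells. In the first count simulation, also requiring a fold change above 1.25 cut the false positives from 32% to 0.2%. But the plan sets no such threshold, and with 50 cells or a low-expression gene the same filter left 6–8%.

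Third, the largest figures are extreme. Under the count model used here, ICC 0.05 needs a visit-to-visit CV of about 28% at gene mean 1 and about 105% at mean 0.05, so one ICC for all genes is unrealistic. That is fair: the 7,107 is the top of an illustrative range, and the count simulations (8–32%) are the better guide.

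Fourth, 1.68 SD need not be a large biological change. In the first simulation case it corresponds to about a 27% change in expression (21% at N = 7). This also stands, so the reworded sentence should say what the effect is large relative to. It still applies to one gene, before any correction over 20,000.

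Finally, this is a pilot seeking candidate biomarkers. That is a reason not to ask for more patients. It does not justify claiming statistical sufficiency from cell counts.

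**Conclusion.** The concern holds. The sufficiency statement is wrong whichever test is chosen later: the independent information on each CBD contrast is 5–7 within-patient changes. The plan also names no unit of analysis or patient-level term for the p-values in its primary outcome. This should be corrected before analysis.

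The size depends on assumptions that the documents cannot settle. A cell-level test at nominal 5% would err about 6–29% of the time with 50 cells of a type per sample and 11–70% with 500, for ICC 0.001 to 0.05. The excess disappears only if patient-by-visit variation is essentially zero. Multiplicity control alone does not remove it.

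**What to change.** - **Keep** pooled cells for clustering and annotation.
- **Under CBD biomarker extraction, name the test and the unit.** For each contrast (baseline to month 1, baseline to month 2), sum counts to one pseudobulk profile per patient, visit and cell type. Test with patient as a blocking factor in a negative-binomial or moderated-t model. A mixed model with random effects for both patient and sample is an alternative; a patient intercept alone would leave the visit-to-visit variation in the error.
- **Control the false discovery rate** over the approximately 20,000 genes.
- **Run the inflammation-marker regression on the same patient-by-visit units**, allowing for repeated visits by the same patient.
- **Replace the sufficiency sentence**, for example: *Inference on CBD effects rests on 5–7 paired within-patient changes; it is exploratory and can detect only effects that are large relative to the SD of those changes.*

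The cost is analysis wording and standard free software, with no new patients or samples. Fewer genes will reach significance, and the sample-size statement becomes less favourable. The change does not supply a control group: a valid before/after change still cannot be attributed to CBD alone.
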